## **10. ETHICAL CONSIDERATIONS**

### **10.1 Regulation statement**

This study will be conducted according to the principles of the Declaration of Helsinki (version 2013, Fortaleza, Brazil) and in accordance with the Medical Research Involving Human Subjects Act (WMO).

### **10.2 Recruitment and consent**

Eligible patients will be recruited from a surgery waiting-list of the Heartcenter. Since only healthcare providers with a treatment-relationship with the patient have access the patient record file, the treating physician will be asked to contact the patient for his/her willingness to participate in this study. After the patient gives permission to be contacted by the investigator ([name]), the investigator will contact the patient by phone with additional information about the study to inquire if the patient is interested in study participation. And if so, patient information will be sent to their home address. Patients will be then given 7 days to read the patient information and to consider the study participation. After this 7-day period, the patients will be contacted again by the aforementioned investigator. If they are willing to participate, an informed consent form will be handed out at clinical admission for signing.

### **10.3 Benefits and risks assessment, group relatedness**

The used VR device has a risk for inducing, eye fatigue, nausea or disorientation. However, the potential benefits of reducing post-operative pain and anxiety and shortening post-surgical recovery time, outweigh these risks.

### **10.4 Compensation for injury**

The investigator (AmsterdamUMC) has a liability insurance which is in accordance with the legal requirements in the Netherlands (Article 7 WMO). The Medical Ethical Commission granted exemption for a damage/injury insurance in accordance with the WMO.

### **10.5 Incentives**

The subjects will receive no financial compensation or other incentives.

## 11. ADMINISTRATIVE ASPECTS, MONITORING AND PUBLICATION

### 11.1 Handling and storage of data and documents

The participant's identity will remain confidential. His or her name will not be published and will not be disclosed to anyone outside the research group. All personal details and other identifiable data provided or collected during this study will be kept in the strictest confidence. Participants will be assigned a code number following their first contact with the researcher. This number will be used throughout the project and will be the only identifier on all data. No identifiable (e.g. name etc.) of participants will be revealed at scientific meetings, conferences, presentations, publications or any other vehicles of public communication. In any such publication arising from this research the individual results will not be identifiable. Only the research team will have access to the collected data.

- Each researcher will store documents bearing identifiable and personal information in a locked cabinet with access strictly restricted to members of the research group.
- All computerised data/information will be stored on pass-word protected computers, to which only a member of the research team has access.
- Code numbers will be used for all computerised data/information collected. These data are therefore stored in a coded fashion.
- All gathered data/information will be stored for the duration of the study. It will then be kept in a locked cabinet for up to 15 years

### 11.2 Amendments

Amendments are changes made to the research after a favourable opinion by the accredited METC has been given. All amendments will be notified to the METC that gave a favourable opinion.

A 'substantial amendment' is defined as an amendment to the terms of the METC application, or to the protocol or any other supporting documentation, that is likely to affect to a significant degree:

- the safety or physical or mental integrity of the subjects of the trial;
- the scientific value of the trial;
- the conduct or management of the trial; or
- the quality or safety of any intervention used in the trial.

All substantial amendments will be notified to the METC and to the competent authority.

Non-substantial amendments will not be notified to the accredited METC and the competent authority, but will be recorded and filed by the investigators.

### **11.3 Annual progress report**

The investigator will submit a summary of the progress of the trial to the accredited METC once a year. Information will be provided on the date of inclusion of the first subject, numbers of subjects included and numbers of subjects that have completed the trial, serious adverse events/ serious adverse reactions, other problems, and amendments.

### **11.4 Temporary halt and (prematurely) end of study report**

The investigator will notify the accredited METC and the competent authority of the end of the study within a period of 90 days. The end of the study is defined as the last patient's last visit.

The investigator will notify the METC immediately of a temporary halt of the study, including the reason of such an action.

In case the study is ended prematurely, the investigator will notify the accredited METC and the competent authority within 15 days, including the reasons for the premature termination.

Within one year after the end of the study, the investigator will submit a final study report with the results of the study, including any publications/abstracts of the study, to the accredited METC and the Competent Authority.

### **11.5 Public disclosure and publication policy**

This project is sponsored by Healthy Mind VR providing the needed VR devices for this study. Healthy Mind VR will be mentioned in the acknowledgements at publication and the Healthy Mind device will be mentioned in the study materials. Further, no special arrangements are made regarding the disclosure of publication material and will be disclosed unreservedly.

### **11.6 Monitoring and Quality Assurance**

Monitoring of the conduct of the study will be done by the Clinical Monitoring Center (CMC) of the AmsterdamUMC. The CMC performs quality control measurements to ensure protection of the rights, safety and well-being of the research subjects and

scientific quality of the research data. After approval of the protocol by the METC the investigators will have an intake appointment with the CMC to prepare a monitoring plan. The monitoring visits will be planned and the frequency of these visits will be conform the NFU-standards depending on the risk-stratification and duration of the study.

## 12. STRUCTURED RISK ANALYSIS

### 12.1 Potential issues of concern

#### a. Level of knowledge about mechanism of action

The software on the Healthy Mind VR device puts patients in immersive experiences in VR to distract them from reality using advanced psychological principles like medical hypnosis. By using the brain's cognitive and affective capacities, pain pathways are modulated through combined visual and auditory stimulations, attention diversion and relaxation.

#### b. Previous exposure of human beings with the test product

Similar studies in which subjects were exposed to a similar product were mainly performed in pediatric patient populations. In all these studies, the used VR devices seemed to be an effective tool in pain and anxiety reduction in these patients. **[10]**

Regarding the specific Healthy Mind VR device, there are no published studies yet. However, there are several ongoing clinical trials in France and Switzerland with the Healthy Mind VR device and similar VR distraction therapy devices. **[11-13]**

#### c. Can the primary or secondary mechanism be induced in animals and/or in *ex-vivo* human cell material?

Not applicable.

#### d. Selectivity of the mechanism to target tissue in animals and/or human beings

Not applicable.

#### e. Analysis of potential effect

Potential adverse effects of the Healthy Mind VR device are nausea and dizziness due to non-adherence to the virtual relaxation technique. This could be related to lacking physical adaptation which can potentially result in cyber-sickness. However, the Healthy Mind software is optimized to minimize these adverse effects by avoiding constant movement and using static teleportation when moving to other digital environments. Furthermore, participants in this study will be excluded from further participation as soon as the above mentioned symptoms are noticed. Additionally we would like to address that these potential symptom are very unlikely to result in significant (lasting) damaging effect.

f. Pharmacokinetic considerations

Not applicable.

g. Study population

The study population consists of patients which are 18 years or older of age and have undergone an uncomplicated surgical CABG procedure. All included subjects are on the general clinical ward and are in stable condition.

h. Interaction with other products

Not applicable.

i. Predictability of effect

Not applicable.

j. Can effects be managed?

As mentioned above, the potential adverse effects in this study are nausea and dizziness. These effects can be effectively managed when observed. The device will be tuned off immediately and common management for these adverse effects will be applied. This will be either expectant policy or supplementation of commonly used anti-emetics.

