##### 4.3 Exclusion criteria

A potential subject who meets any of the following criteria will be excluded from participation in this study:

- Major comorbidities besides coronary artery disease
- Complicated surgical procedure
- Hearing and/or visual impairments
- Psychiatric impairments
- Complaints of vomiting and nausea
- History of epilepsy
- Claustrophobia
- Facial wounds and skin defects at site of application
- Patients placed in clinical isolation
- Readmission to the intensive care unit

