### **7.4 Withdrawal of individual subjects**

Subjects can leave the study at any time for any reason if they wish to do so without any consequences. The investigator can decide to withdraw a subject from the study for urgent medical reasons.

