### **7.5 Replacement of individual subjects after withdrawal**

Upon withdrawal of a subject, the data collected will not be used for the study and will be deleted.

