#### **7.6 Follow-up of subjects withdrawn from treatment**

Not applicable.

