#### **7.7 Premature termination of the study**

Study participants can withdraw their consent at any time during the study. Patients that experience eye fatigue, nausea or disorientation will not be included in this study. In addition, since all the elements of this study are harmless and carry no significant risks, it is unlikely that premature termination will occur during the study.

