### **8.3 Follow-up of adverse events**

All AEs will be followed until they have abated, or until a stable situation has been reached. Depending on the event, follow up may require additional tests or medical procedures as indicated, and/or referral to the general physician or a medical specialist. SAEs need to be reported till end of study within the Netherlands, as defined in the protocol

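### Removing symptomatic participants from the study, and not only from VR, would cost mainly VR-arm patients after randomisation, with no outcome follow-up or as-randomised analysis stated

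*Combined protocol and SAP*

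**What the plan says.** The rule on device symptoms appears twice in the same words, in section 6.3 and in section 12.1 item e: "participants in this study will be excluded from further participation as soon as the above mentioned symptoms are noticed". Section 7.7 adds: "Patients that experience eye fatigue, nausea or disorientation will not be included in this study". Section 12.1 item j gives the clinical response: "The device will be tuned off immediately and common management for these adverse effects will be applied".

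The surrounding sections say the following.

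- **Timing (7.2, 7.3).** Allocation happens after surgery, on return to the ward. The intervention group has therapeutic VR sessions on days 1, 2 and 3; the control group has none. The trial is unblinded.
- **Entry criteria (4.3).** The exclusion list, which applies to both arms, includes "Complaints of vomiting and nausea".
- **Withdrawal (7.4, 7.5).** Patients may leave at will, and "The investigator can decide to withdraw a subject from the study for urgent medical reasons". Then: "Upon withdrawal of a subject, the data collected will not be used for the study and will be deleted".
- **Follow-up (7.6).** The section headed "Follow-up of subjects withdrawn from treatment" is marked as not applicable.
- **Safety (8.3).** "All AEs will be followed until they have abated, or until a stable situation has been reached".
- **Analysis (9.1).** Rank-sum tests compare the groups on each of days 1 to 3 and on mean values. No analysis population and no handling of missing data are given.

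**The concern.** A participant who feels sick in the headset has to stop using it. Nothing about that requires the trial to stop measuring pain, anxiety and recovery. If the rule is followed as it most naturally reads, randomised patients leave the comparison because of a reaction to the treatment under test, and they leave mainly from one arm. The patients left in the VR arm are then those who tolerate VR, compared with a nearly complete control arm.

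The trigger is also loose. Symptoms only have to be noticed, with no severity threshold, by staff who know the allocation.

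At stake is the main comparison on NRS, QoR-15, STAI-6 and analgesic use. If removed patients would have scored worse than those who stay, VR looks better than it is. That is plausible for recovery scores in someone with nausea or dizziness. If they would have scored better, VR looks worse than it is. If they do not differ, the only cost is a smaller arm. Outcomes that were never collected, or were deleted, cannot be recovered at the analysis stage.

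**Working it through.** **1. Reproduce the planned power.** Inputs are the Table 1 proportions for NRS categories 1 to 8 (section 4.4), 50 per group, two-sided alpha 0.05. The means are 4.770 (group 1, SD 1.94) and 3.548 (group 2). I take group 1 as control, which the table does not state.

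P(X<Y) + ½P(X=Y) = 0.2395 + ½ × 0.1439 = 0.3115 (stated: 0.311).

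Power = Φ[(|0.3115 − 0.5| − 1.96√V0)/√V1], with V0 the tie-corrected null variance (0.003247) and V1 the variance under the alternative (0.002718):

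(0.1885 − 1.96 × 0.05698)/0.05214 = 1.47, so power is 93.0%. Simulating the tie-corrected test gives 92.7%. The plan's 92.7% is reproduced.

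**2. Bias under selective removal.** The documents give no symptom rate and no outcome difference for removed patients, so both are assumptions. Set no true effect (both arms on the group 1 distribution, 50 each). Remove VR patients with a probability logistic in NRS, tuned so that a given share is removed and their mean NRS is 1 or 2 points above that of those who stay. Drop their NRS completely and remove no controls. The VR mean then shifts by share × difference. With 200,000 runs per case, simulation error is under 0.1 point.

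| Share removed | NRS difference | Shift in VR mean | Two-sided type I error | Of which in favour of VR |
|---|---|---|---|---|
| 5% | 1 | 0.05 | 5.2% | 3.3% |
| 5% | 2 | 0.10 | 5.6% | 4.3% |
| 10% | 1 | 0.10 | 5.7% | 4.4% |
| 10% | 2 | 0.20 | 7.6% | 6.9% |
| 20% | 1 | 0.20 | 7.5% | 6.8% |
| 20% | 2 | 0.40 | 15.6% | 15.5% |

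**3. Opposite direction.** If removed patients have lower NRS by the same amounts, the two-sided error is essentially the same but the excess favours control. At 10% and 2 points, about 7.0% of trials falsely favour control and 0.7% falsely favour VR.

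**4. Some controls removed too.** With controls removed at half the VR rate and the same NRS difference, the range is 5.0% to 7.5%. With equal removal it is about 5%.

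**5. Earlier data kept.** Suppose 7.5 does not apply, removals are spread evenly over days 1 to 3, and NRS is missing from the day of removal. On days 1, 2 and 3 the error is then 5.2%, 6.1% and 7.6% (10%, 2 points) or 5.9%, 9.0% and 15.6% (20%, 2 points). The day 3 figures assume that the full difference lasts until day 3.

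**6. Removal unrelated to outcome.** There is no bias. Power with 48, 45 or 40 VR patients against 50 controls is about 92%, 91% or 89%.

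**7. Cost of keeping these patients in.** In the worst case those who stop VR gain nothing, so the VR arm is a mixture f × group 1 + (1 − f) × group 2. For f = 5%, 10% and 20%, power is 89.8%, 86.1% and 76.8%. If they keep half the benefit it is about 91%, 90% and 86%.

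Only NRS can be computed; the documents give no distribution for QoR-15 or STAI-6.

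**The case against.** The strongest reply is that the rule stands only in text about device risk, where participation may mean further VR sessions. Item 12.1j turns the device off and treats the symptom, and does not say that assessments end. The sentence in 7.7 is worded as a condition of entry. On that reading the 6-week call would still take place and nothing would be lost. This reading cannot be excluded. It is the less natural one, because 7.6, where continued follow-up would be described, is marked as not applicable, and no other section says that assessment continues.

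Other points stand in part:

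- A reader might infer that data from VR failures will be deleted. That follows only if the exclusion counts as a withdrawal. Section 7.4 covers patient choice and urgent medical reasons, and symptoms managed by waiting or with anti-emetics are not clearly urgent.
- A reader might infer that only the VR arm can lose patients. The wording covers all participants, and nausea is an exclusion criterion for both arms, so a control with ordinary post-operative nausea could be caught. Symptoms at the preoperative test-use come before randomisation and do not unbalance the arms; that test may also filter out some susceptible patients.
- Safety is not neglected: adverse events are followed under 8.3.

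**Conclusion.** The concern holds as a rule that should be changed, with medium confidence. Read naturally, 6.3 and 12.1e remove randomised patients mainly from the VR arm, 7.6 provides no outcome follow-up for them, and 9.1 does not say that they are analysed as randomised.

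A reader might go further and conclude that the trial is biased in favour of VR. The documents do not support that: they say nothing about how removed patients' outcomes compare with those of patients who stay, so both direction and size are open. The type I error of about 5.2% to 15.6% rests on an assumed 5% to 20% removal, a 1 or 2 point NRS difference, no control removals and complete loss of removed patients' NRS. Five of the six cases are below 8%. Only the most severe is large, and it falls to 7.5% if controls are removed at half the VR rate. If removed patients do not differ from those who stay, there is no bias.

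**What to change.** Separate stopping the device from leaving the study:

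- **6.3 and 12.1e:** on device symptoms VR use is stopped; the participant stays in the study and all outcome assessments continue, including the 6-week call.
- **7.6:** put the same statement in place of the present entry.
- **7.5:** stopping VR is not a withdrawal, and the data are kept.
- **9.1:** all randomised patients are analysed in their allocated arm.
- **7.7 and the nausea and vomiting criterion in 4.3:** limit both to the period before randomisation, so that neither can be used to remove a patient later.

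These are wording changes, and the assessments are already planned for every participant. Safety is unaffected, since 12.1j already stops the device and treats the symptom. The price is dilution: at worst, power falls to about 90%, 86% or 77% when 5%, 10% or 20% of the VR arm stop VR. In return the result estimates the effect of offering VR to these patients, including those who cannot tolerate it.

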## 12.2 Synthesis

Altogether, there are no significant risks to this study. The software of the device is optimized to reduce the potential adverse effects being nausea and dizziness. Also adequate management strategies are available for these potential effects. Since these potential effects are highly unlikely to result in significant (remaining) damage, the potential benefits of reducing pain and anxiety in the post-surgical phase outweigh these.

